5.4 Screen Failures

Screen failures are defined as participants who consent to participate in the clinical trial but are not subsequently randomly assigned to the study intervention or entered in the study. A minimal set of screen failure information is required to ensure transparent reporting of screen failure participants, to meet the Consolidated Standards of Reporting Trials (CONSORT) publishing requirements (for NIH studies) and to respond to queries from regulatory authorities. Minimal information includes demography, screen failure details, eligibility criteria, and any serious adverse event (SAE).

5.5 Strategies for Recruitment and Retention

For clinic-based recruitment, caregivers will be introduced to the study in one of two primary ways: 1) in person, while attending a clinic appointment with an adult patient or 2) study flyers posted in the clinic rooms. Trained research assistants at both UVA and Pitt will be available to meet potential participants in-clinic or discuss the study by phone, and the study team members also have robust connections with clinic staff to support participant recruitment as well.

For recruitment via participant registry outreach, caregivers will be introduced to the study in one of three primary ways: 1) by telephone outreach, 2) by email and/or letter outreach, or 3) by matching with our study via the Pitt+Me research study database. The Caregiver Research Registry, part of the Pitt Center for Social & Urban Research Survey Research Program, comprises over 1,000 self-identified caregivers who are representative of the Western Pennsylvania population and are willing to participate in research studies. We will also reach out to care partners who have indicated willingness to be contacted in research studies via the Pitt Alzheimer's Disease Research Center (ADRC). We will also recruit individuals enrolled in the *Contact Database for UVA Cancer Center Catchment Area Survey Participants* (UVA IRB-SBS 3993). This contact database includes participants who opted into being recontacted about future studies when they completed the UVA Cancer Center catchment area survey (as has been approved by UVA IRB-HSR previously, see HSR 22747 exempt protocol as example).

We will also utilize online advertisement and promotion methods to distribute information about our study. This may include posts and/or advertisements through Facebook, Instagram, Reddit, Twitter, and other websites pertinent to family caregiving and digital

health research. Study information may also be distributed through pertinent listservs and newsletters by community and partner organizations. Potentially interested individuals will be directed to our study website and provided with contact information for study staff.

6 STUDY INTERVENTION

6.1 Description of Study Intervention(s)

Type	Name	Investigational or Standard of Care (SOC)	Description
Behavioral (e.g., Psychotherapy, Lifestyle Counseling)	Sleep Healthy Using the Internet (SHUTi)	Interventional	SHUTi is a self-guided, interactive, and tailored Internet-based Program that incorporates the primary tenets of face-to-face cognitive behavioral therapy (CBT) for insomnia. Content is presented in six Cores, with a new Core available seven days after completion of the previous Core. SHUTi relies on user-entered sleep diaries to track progress and Tailor recommendations. Each Core parallels the structure of traditional Weekly face-to-face CBT-I sessions and includes: 1) examination of Core objectives, 2) review and feedback on homework and sleep diary from the prior week, 3) teaching new intervention material, and 4) assignment of homework. Intervention content is enhanced through goal-setting, graphical feedback based on the participant's symptoms, animations and illustrations to enrich comprehension, quizzes to test and enhance user knowledge, vignettes to promote identification with material, and video-based expert explanations.

6.2 Registration, Randomization and Blinding

All participants must sign the consent form prior to determination of eligibility for this study. This study does not involve any blinding or masking procedures. Subjects will be told which treatment they are receiving.

7 STUDY CLOSURE, STUDY INTERVENTION DISCONTINUATION AND PARTICIPANT DISCONTINUATION OR WITHDRAWAL

7.1 Study Discontinuation and Closure

This study may be temporarily suspended or prematurely terminated if there is sufficient reasonable cause. Written notification, documenting the reason for study suspension or termination, will be provided by the suspending or terminating party to sponsor. If the study is prematurely terminated or suspended, the Principal Investigator (PI) will promptly inform the Institutional Review Board (IRB) and sponsor and will provide the reason(s) for the termination or suspension. Study participants will be contacted, as applicable, and be informed of changes to study visit schedule.

Circumstances that would warrant termination or suspension include, but are not limited to

- Determination of unexpected, significant, or unacceptable risk to participants
- Demonstration of efficacy that would warrant stopping
- Insufficient compliance to protocol requirements
- Data that are not sufficiently complete and/or evaluable
- Determination that the primary endpoint has been met
- Determination of futility
- Change in funding status

Study may resume once concerns about safety, protocol compliance, and data quality are addressed, and satisfy the sponsor, IRB, Data and Safety Monitoring Committee (if applicable) and/or Food and Drug Administration (FDA) (if applicable).

Participants receiving study treatment at the time of study discontinuation should complete procedures described in *section 7.4*.

7.2 Participant Discontinuation/Withdrawal

Participants are free to withdraw from participation in the study at any time upon request.

A participant's study treatment would be discontinued for the following reasons:

- Significant study intervention non-compliance
- If any clinical adverse event (AE), laboratory abnormality, or other medical condition or situation occurs such that continued participation in the study would not be in the best interest of the participant (see *section 7.3* for dose-limiting toxicities)
- Disease progression which requires discontinuation of the study intervention
- If the participant meets an exclusion criterion (either newly developed or not previously recognized) that precludes further study participation
- Participant unable to receive study intervention.
- Participant decision to withdraw from study treatment and/or the study
- Initiation of prohibited intervention or medication

The reason for participant discontinuation or withdrawal from study treatment will be recorded. Participants who sign the informed consent form but do not receive the

study intervention may be replaced. Participants who sign the informed consent form, and receive the study intervention, and subsequently withdraw, or are withdrawn or discontinued from the study, will be replaced. Participants that withdraw from the study (not only from study treatment, but all study follow-up) will not be contacted for any further study visits.

A participant will be considered lost to follow-up if he or she fails to complete pre-assessment and is unable to be contacted by the study site staff.

The following actions must be taken if a participant fails to complete assessments:

- The site will attempt to contact the participant and counsel the participant on the importance of maintaining the program and ascertain if the participant wishes to and/or should continue in the study.
- Before a participant is deemed lost to follow-up, the investigator or designee will make every effort to regain contact with the participant.
- These contact attempts should be documented in the study file.
- Should the participant continue to be unreachable, he or she will be considered to have withdrawn from the study with a primary reason of lost to follow-up.

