emotional and physical well-being.^{2,3} Support from family members to seriously ill individuals is critical to the sustainability of the U.S. healthcare system,¹⁴ but it places a significant strain on these caregivers. Insomnia is among the most common, distressing, and impairing psycho-physiological issue for caregivers, who report this problem more commonly than non-caregivers.^{15,16} Compared to about 33-50% in the general population,¹⁷ up to 90% of caregivers report sleep impairment,¹⁸ although rates have varied by contexts – for example, 27% in Parkinson's caregivers,¹⁹ 50-75% in cancer,²⁰⁻²² and 63-68% in dementia.^{18,23,24} Sleep impairment contributes to caregivers' anxiety, depression, and physical morbidity,^{21,25-29} which affect caregivers more severely than those in the general population.³⁰⁻³³ Moreover, caregivers' poor sleep also ultimately affects their care recipients. Because it increases their distress, sleep-deprived caregivers are more likely to exhibit harmful caregiving behavior³⁴ and less able to meet the practical and social-emotional needs of the care recipient.^{35,36} Additionally, care recipients' sleep disturbance is interrelated with their caregivers'.^{37,38} Accessible and effective insomnia interventions for caregivers are therefore important to the well-being of both caregivers and care recipients. Although such interventions are effective, they suffer from low enrollment, high dropout, and limited reach to caregivers who already have inadequate healthcare access, like caregivers from lower SES or those in rural areas.³⁹⁻⁴³ Digital health interventions can lower barriers to entry to supportive care for caregivers as they are conveniently accessible anywhere and anytime from an Internet-enabled device. Indeed, caregivers express strong interest in Internet interventions because of their convenience.⁴⁴⁻⁴⁶ Multiple existing, efficacious digital health interventions may effectively address caregivers' psychosocial needs. For example, Sleep Healthy Using the Internet (SHUTi), developed by [name], is an NCI designated research-tested intervention that delivers cognitive-behavioral therapy for insomnia (CBT-I).^{47,48} Most digital health interventions tested among caregivers, however, have been developed *de novo* for specific caregiving contexts.⁴⁹⁻⁵⁴ Tailoring interventions in this way is rooted in behavior change theory: tailoring to a user's characteristics increases information salience, which increases a user's attention to information, which ultimately increases the likelihood that the information will motivate behavior change.⁸ When tested empirically, tailoring typically adds only small gains in outcomes relative to generic materials, although gains are typically maintained over time.^{10,55,56} The decision to tailor, and how to tailor, must balance expected benefits of increased specificity against reduced reach and increased costs (time and financial). The implicit assumption underlying existing research – where *de novo* interventions are developed for caregivers – is that caregivers have different deficits, risk factors, and needs from non-caregivers. There is reason to believe this is true and that caregiving has unique psychological and environmental factors that would affect use and impact of insomnia interventions specifically, and digital health interventions broadly. Specific to insomnia interventions, caregivers' insomnia can be perpetuated by worry about the negative impact of sleep loss on their ability to meet the demands of caregiving and a feeling of helplessness to improve their sleep due to their caregiving responsibilities.^{22,28,57} Indeed, caregivers do frequently need to organize their sleep around the needs of the care recipient³⁸ and often need to support the care recipient at night with symptom management or nighttime behavioral issues.^{22,28} When considering digital health interventions more broadly, research repeatedly highlights primary barriers to caregivers' help-seeking being their self-sacrifice – the de-prioritization of caregivers' own needs behind the needs of the care recipient, particularly prominent among high-intensity caregivers – and caregivers' guilt when they do prioritize their needs.⁵⁸⁻⁶¹ Caregivers' often busy and chaotic schedules – also particularly true of high-intensity caregivers – likewise commonly get in the way of their ability to commit to consistently

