3 OBJECTIVES AND ENDPOINTS

Objectives	Endpoints
Primary	
To test the association of SHUTi engagement with caregiving context.	Level of engagement: non-users (i.e., completed no Cores), incomplete users (i.e., completed 1 to 3 Cores), and complete users (i.e., completed 4 to 6 Cores)
Secondary	
To describe caregivers' barriers and motivations for SHUTi engagement	
 • Open-ended feedback about SHUTi • SHUTi utility and barriers: Internet Intervention Utility, Evaluation, and Adherence questionnaires
To test the association of SHUTi efficacy on known cognitive mechanisms with caregiving context.	
Cognitive mechanisms of change targeted by SHUTi
 
 • Sleep beliefs: Dysfunctional Beliefs and Attitudes about Sleep scale • Sleep control: Sleep Locus of Control Scale

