8 STUDY ASSESSMENTS AND PROCEDURES

8.1 Study Materials and Methods

Participating caregivers will be instructed on how to complete the pre-assessment battery of online questionnaires using either computer or mobile device as the participant prefers. Estimated completion times are 30 minutes for questionnaires. Upon completing questionnaires, participants will complete 10 daily sleep diaries within 14 days. Participants will be compensated \$40 upon pre-assessment completion.

After participants complete pre-assessment, they will receive access to SHUTi. Participants will be emailed a unique username and password in order to log on and securely access SHUTi for 9 weeks. The intervention can be accessed via an Internet enabled device, including a computer, tablet, or smartphone. At the start of week ten, regardless of intervention progress, participants will be instructed to complete their online post assessment.

Non-users' (i.e., those who completed 0 SHUTi Cores) post-assessment will include an open-ended survey regarding barriers to SHUTi adoption, the extent to which barriers were related to caregiving, and what modifications may have increased their motivation to try SHUTi. Users' (i.e., those who completed 1 or more SHUTi Cores) post-assessment will include an open-ended survey assessing SHUTi usage barriers and motivations, the extent to which these were related to caregiving, and how tailoring may improve usage by increasing salience to caregivers. SHUTi users will also complete 10 daily sleep diaries in 14 days as part of post-assessment. Participants will be compensated \$40 upon post-assessment completion.

Caregivers who agree to be contacted for follow-up will be returned a concise report of results from the analyses as part of synthesized member checking procedures, where caregivers will be asked to review the report and comment on how results compare/contrast with their experiences and needs.

Sources of research materials:

The sources of research material will include:

- (1) self-report questionnaires completed over the Internet (including caregiving-related user- and environment characteristics; as well as demographics, sleep, self-efficacy and other health/psychosocial constructs);
- (2) telephone interview to inquire about sleep problems, insomnia treatment history, and computer/Internet usage;

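### Section 7.2 makes undefined non-compliance a reason to stop SHUTi without exempting low Core use, which is itself part of the primary endpoint

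*Combined protocol and SAP*

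**What the plan says.** Section 7.2 says that a participant's "study treatment would be discontinued for the following reasons", and the first reason listed is "Significant study intervention non-compliance". No threshold, time window or definition follows, there or elsewhere in the protocol.

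Section 3 defines the primary endpoint as level of engagement: "non-users (i.e., completed no Cores), incomplete users (i.e., completed 1 to 3 Cores), and complete users (i.e., completed 4 to 6 Cores". The assessment table in 8.1 takes Core completion from the SHUTi platform. Section 10.2 plans for 22%, 33% and 45% of the sample in the three levels.

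Under 8.1, participants can "securely access SHUTi for 9 weeks", and the post-assessment is requested at the start of week ten however far they have got. Under 6.1, Cores are released one at a time, "with a new Core available seven days after completion of the previous Core".

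**The concern.** In most trials, stopping treatment for poor compliance is a routine safeguard. Here, compliance with the intervention is the outcome. SHUTi is self-guided, so not completing Cores is the most natural meaning of failing to comply with it, and up to 22% + 33% = 55% of the sample is expected in the two lower levels.

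If staff closed an account for low use before week 9, the Core count would record when access was withdrawn as well as how far the caregiver would have gone. That holds even if everyone stays in the model. A cut unrelated to the predictor pulls the odds ratio towards 1. A related cut can bias it in either direction and can produce an association where none exists. A classification cut short cannot be recovered afterwards.

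**Working it through.** **1. Can an early cut change the outcome level?** Cores 2, 3 and 4 open at best 7, 14 and 21 days after Core 1 is completed (6.1), and access lasts 9 × 7 = 63 days (8.1). A caregiver who finishes Core 1 by about day 63 − 21 = 42 can still reach Core 4 and count as a complete user. One with no Cores can become a user until day 63. So a cut before those days can change the level.

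**2. The plan's own figure.** Section 10.2 states a minimum detectable odds ratio of 2.9 at N = 100, 80% power and α = .05 (two-sided assumed). The Whitehead variance with a 50/50 predictor is V = n₁n₂N / [3(N+1)²] × (1 − Σp³).

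- Σp³ = .22³ + .33³ + .45³ = .1377
- V = 50 × 50 × 100 / (3 × 101²) × .8623 = 7.04
- Minimum odds ratio = exp[(1.960 + 0.842)/√7.04] = 2.87, which agrees with 2.9
- Power at 2.9 = Φ(ln 2.9 × √7.04 − 1.960) = 81%

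**3. Cells before any cut.** An odds ratio of 2.9 with margins 22/33/45 and a median split on strain (as in the 10.2 table) gives non-user/incomplete/complete probabilities of .133/.289/.579 for low strain and .307/.371/.321 for high strain.

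**4. Applying a cut.** In each strain group a share c of would-be incomplete users ends as non-users, and a share kc of would-be complete users ends as incomplete:

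- non-user + c × incomplete
- incomplete × (1 − c) + kc × complete
- complete × (1 − kc)

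k = 0 means that only would-be incomplete users are cut; k = 1 means that would-be complete users are cut equally often. The proportional-odds model is refitted to the new cells, and power comes from V with the new margins at N = 100. Every value of c is an assumption. A would-be incomplete user stopped after completing a Core keeps the same level, so c counts only cuts that change the level.

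| Cut rate, low vs high strain | k = 0: OR; power | k = 1: OR; power |
|---|---|---|
| none | 2.90; 81% | 2.90; 81% |
| 10% vs 10% | 2.84; 79% | 2.69; 76% |
| 5% vs 15% | 3.03; 84% | 3.27; 89% |
| 15% vs 5% | 2.66; 74% | 2.2; 57% |

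Check of one cell (15% vs 5%, k = 0): margins .251/.299/.450 give V = 7.08, and Φ(ln 2.66 × √7.08 − 1.960) = 74%.

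**5. No true association.** With 5% vs 15%, k = 0 gives an odds ratio of about 1.06 and two-sided rejection of 5.3%; k = 1 gives 1.20 and 7.8%. Cuts unrelated to strain leave the odds ratio at 1.00 and rejection at 5%.

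**The case against.** The strongest reply is that the design already settles the matter. Section 8.1 fixes 9 weeks of access, asks everyone for a post-assessment and gives people with no Cores their own survey. Section 10.2 budgets for them. The 7.2 list looks generic: neighbouring bullets mention laboratory abnormalities and dose-limiting toxicities. The schedule of activities has no progress check between access and post-assessment, and no text describes staff reviewing Core counts or closing accounts. All of this stands, and it makes use of the bullet against low users unlikely. It does not cancel the bullet, which remains a stated rule in the protocol that two sites follow.

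The reply also limits the size. A low-use rule would mostly reach people making little progress. Section 2.2.1 reports that more than 90% of those who complete Core 4 go on to finish all six. Core 6 opens 35 days after Core 1, so they need Core 1 by about day 63 − 35 = 28. If that pattern holds for caregivers with 9 weeks of access, people who start later and still become complete users are under 10% of complete users. The k = 0 column is therefore the more realistic one. A rule applied very early could still catch slower starters, so k = 1 is an upper case.

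Nor do the documents show that cuts would differ by strain. Section 2.2 says that crowded schedules "likewise commonly get in the way of their ability to commit to consistently" take part. That supports a link between caregiving load and low use, which is the hypothesis under test, but says nothing about staff decisions.

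A reader might go further and infer that low users are removed and replaced, emptying the lower levels. The text does not support this. Non-compliance ends study treatment, whereas replacement applies to those who receive SHUTi "and receive the study intervention, and subsequently withdraw, or are withdrawn or discontinued from the study, will be replaced". Someone who cannot be contacted is treated as having left ("Should the participant continue to be unreachable, he or she will be considered to have withdrawn from the study"), but that follows from missed assessments, not from low Core use.

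A reader might also infer that people who leave are dropped from the Aim 1 model, because 10.3.1 names no analysis set. Nothing says so. Their predictors are collected before access, their Core counts are on the platform, and the design points to keeping them.

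**Conclusion.** The point holds as a minor defect. Section 7.2 states a rule that, read literally, lets staff end access for behaviour that the trial is meant to observe, and no text exempts low Core use. If the bullet is never applied, there is no effect.

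If it is applied at the assumed 5% and 15% by strain, with a true odds ratio of 2.9, the fitted value is about 3.03 (reversed: 2.66, power 74%) with only would-be incomplete users cut. It reaches 3.27 (reversed: 2.2, power 57%) if would-be complete users are cut equally. Rejection under no association is 5.3% to 7.8%. These figures rest on assumed cut rates, a 50/50 strain split and N = 100. The plan's minimum detectable odds ratio of 2.9 reproduces and is not in question.

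The missing Aim 1 analysis set in 10.3.1 is something to clarify, not an error.

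**What to change.** In 7.2, delete the non-compliance bullet, or add one sentence: low or no Core completion is not non-compliance and never ends the 9-week access.

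As an optional clarification, 10.3.1 could say that everyone given SHUTi access is analysed for Aim 1 at the platform-logged Core count at the end of 9 weeks.

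The cost is one or two sentences and no new data. The only downside of the change to 7.2 is that unused accounts stay open until week 9.

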8 STUDY ASSESSMENTS AND PROCEDURES

8.1 Study Materials and Methods

Participating caregivers will be instructed on how to complete the pre-assessment battery of online questionnaires using either computer or mobile device as the participant prefers. Estimated completion times are 30 minutes for questionnaires. Upon completing questionnaires, participants will complete 10 daily sleep diaries within 14 days. Participants will be compensated \$40 upon pre-assessment completion.

After participants complete pre-assessment, they will receive access to SHUTi. Participants will be emailed a unique username and password in order to log on and securely access SHUTi for 9 weeks. The intervention can be accessed via an Internet enabled device, including a computer, tablet, or smartphone. At the start of week ten, regardless of intervention progress, participants will be instructed to complete their online post assessment.

Non-users' (i.e., those who completed 0 SHUTi Cores) post-assessment will include an open-ended survey regarding barriers to SHUTi adoption, the extent to which barriers were related to caregiving, and what modifications may have increased their motivation to try SHUTi. Users' (i.e., those who completed 1 or more SHUTi Cores) post-assessment will include an open-ended survey assessing SHUTi usage barriers and motivations, the extent to which these were related to caregiving, and how tailoring may improve usage by increasing salience to caregivers. SHUTi users will also complete 10 daily sleep diaries in 14 days as part of post-assessment. Participants will be compensated \$40 upon post-assessment completion.

Caregivers who agree to be contacted for follow-up will be returned a concise report of results from the analyses as part of synthesized member checking procedures, where caregivers will be asked to review the report and comment on how results compare/contrast with their experiences and needs.

Sources of research materials:

The sources of research material will include:

- (1) self-report questionnaires completed over the Internet (including caregiving-related user- and environment characteristics; as well as demographics, sleep, self-efficacy and other health/psychosocial constructs);
- (2) telephone interview to inquire about sleep problems, insomnia treatment history, and computer/Internet usage;
- (3) daily symptom diaries collected over the Internet to track sleep symptoms (e.g., minutes to fall asleep) in order to automatically tailor treatment recommendations; and
- (4) open-ended survey items related to either barriers to SHUTi adoption, the extent to which barriers were related to caregiving, and what modifications may have increased their motivation to try SHUTi (non-users) or SHUTi usage barriers and motivations, the extent to which these were related to caregiving, and how tailoring may improve usage by increasing salience to caregivers (users).

All data will be collected explicitly and exclusively for this study and will be maintained following HIPAA regulations. Data collected through the internet will be obtained through secured means and stored on our private servers. Personal Health Information (PHI) will be stored separately from study data on a different HIPAA compliant server. Only study staff with the requisite IRB-approved Human Subjects Training will have access to participant data.

Surveys will be performed according to the Table below:

Variable / Measure	Outcome measured	Time Point	
		Pre	Post
Screening			
Caregiving	High-intensity caregiving (based on National Alliance of Caregiving intensity index), future duration	Screen	
Internet access	Regular Internet and email access	Screen	
Contact / verification	Age/year of birth, name, zip, phone, email	Screen	
Insomnia	Insomnia Severity Index	Screen	
Sleep	Usual bed/wake times (phase shift), shift work, current psychological/behavioral treatment for insomnia	Screen	
Medical contraindications	Dx'ed with: RLS/PLMD, OSA, narcolepsy, parasomnia, dementia, Alzheimer's, Parkinson's, Huntington's Symptoms of: RLS, OSA Ever/recovered: Stroke, TBI, Brain infection, brain tumor Current: pregnancy/breastfeeding, hyperthyroidism, cancer, respiratory disease Current/managed: Epilepsy Current/3-mo stable: Steroids, amphetamines, stimulants, prescribed sleep medications	Screen	
Psychological/ Psychiatric Contraindications	MINI: Mania/hypomania, Alcohol dependence/abuse, Substance dependence/abuse Dx'ed with psychosis or schizophrenia	Screen	
Covariates			
Sociodemographics	Age, household income, health literacy,	✓	

Health-related Quality of Life	PROMIS: 2-item Global Physical Health	✓	✓
General Distress	Patient Health Questionnaire-4	✓	✓
Predictors: Caregiving-related user characteristics			
Caregiving strain	Pearlin Stress Scale – Caregiving Overload subscale	✓	✓
Caregiving self-efficacy	Pearlin Stress Scale – Caregiving Competence subscale	✓	
Caregiving guilt	Caregiver Guilt Questionnaire – Guilt about doing wrong by the care recipient, guilt about not rising to the occasion as a caregiver, guilt about self-care subscales	✓	
Predictors: Caregiving-related environment characteristics			
Proximity to CR	Whether bedpartner, live together but not bedpartner, other situation	✓	
CR functional status	Modified Barthel Activities of Daily Living [ADL] Index	✓	
CR cognitive status	Pearlin Stress Scale – Cognitive Status subscale	✓	
CR problem behavior	Pearlin Stress Scale – Problematic Behavior subscale (includes night-time problems)	✓	
Caregiving tasks	Involvement in supporting ADL, Instrumental ADL, and nursing tasks	✓	
Changes in caregiving	Single item question (with follow-up open-ended response) if caregiving situation has significantly changed during study		✓
Aim 1 Outcomes: SHUTi engagement (Core completion recorded through SHUTi online platform)			
Core completion	Non-user (no Cores completed); Incomplete user (1-3 Cores); Complete user (4-6 Cores)	Through SHUTi	
Open-ended feedback	Free-response survey items – separate surveys for non-users and users		✓
SHUTi utility and barriers	Internet Intervention Utility, Evaluation, and Adherence Questionnaires – select items		✓*
Aim 2 Outcomes: SHUTi efficacy on known cognitive mechanisms			
Sleep beliefs	Dysfunctional Beliefs and Attitudes About Sleep	✓	✓*
Sleep control	Sleep Locus of Control Scale	✓	✓*
Exploratory: Preliminary Efficacy			
Insomnia severity	Insomnia severity index	✓	✓
Sleep diary metrics	10 days of sleep diaries in 14 day period	✓	✓*

*SHUTi users only

